6.2.8 Subanalyses

A pre-planned subanalysis of the primary outcome will be performed in the group with baseline thiamine deficiency. Thiamine deficiency will be defined as a plasma vitamin B1 level ≤ 7 nmol/L as has been previously described.⁴⁸ The trial is not powered to detect subgroup differences, hence this analysis will be considered exploratory and hypothesis-generating.

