6. SAMPLE SIZE CALCULATION AND STATISTICAL ANALYSIS PLAN

6.1 Sample size calculation

The planned sample size is based on the proposed primary outcome. In this longitudinal repeated measures study design, we have 4 time points, and are interested in measuring the effect of the intervention (thiamine) on the mean level of creatinine at the last time point (72-hours). We hypothesized that at 72-hours, the estimated mean difference (placebo-thiamine) would have similar magnitude as the pilot study's ⁴ observed mean difference (about 0.51). We used a linear mixed-effects model to estimate the parameters of the variance-covariance structure of the repeated measures data and used these estimates in obtaining the effect estimate of the mean difference at each of the 4 time points, with emphasis on 72-hours. We simulated the data using the estimated variance-covariance components from the pilot data which 0.19 for within-subject variance, and 1.3 for between-subject variance, and the estimated mean differences for the 4 time points from the pilot data. These data were put through a linear mixed effects model where linear contrasts were used for estimation at each time point. We then computed the non-centrality parameter and the corresponding F-statistic value. Together with the numerator and denominator degrees of freedom, the estimate of power at each time point was derived. Through different iterations of sample size, at N=80 (40 patients in each arm), we obtained a power of 0.80 at 72-hours. This method of power analysis for linear mixed-effects model was published in 2000.⁴¹ To account for drop-out and to

ensure adequate power at the end of the trial, we will plan to enroll a total of 88 patients (44 per arm).

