6.2 Statistical analysis plan

6.2.1 General considerations

The statistical analyses and reporting will adhere to the CONSORT guidelines.^{42,43} All tests will be two-sided, a p-value < 0.05 will be considered significant, and all confidence intervals will have 95% coverage. All analyses will be conducted on a modified intention-to-treat basis only including participants receiving at least the first dose of the study medications. In a double-blind trial, this approach is unbiased while increasing precision.⁴⁴ The two groups will be compared in relation to baseline characteristics using descriptive statistics.

The persons conducting the statistical analysis will be blinded to the randomized allocation. Groups will be designated as “A” and “B” until all pre-specified analyses are performed and shared with all authors and the Data Safety Monitoring Board.

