6.2.2 Creatinine at 72-hours

Assuming no unbalanced potentially confounding variables (as would be expected in this randomized trial), we will compare repeated measures of creatinine levels at each time point (0h, 24h, 48h, 72h) between arms using repeated measures analysis. A compound symmetry covariance structure will be used. If a patient receives renal replacement therapy or dies before any time point, creatinine levels will be imputed by carrying forward the last known value before the event. Study site will be controlled for as a fixed-effect in the regression model.

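### The exploratory thiamine-deficiency subanalysis compares arms within deficient patients alone, so it cannot show whether the effect differs by deficiency (minor)

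*Protocol*

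**What the plan says.** Section 6.2.8 names a single subanalysis: "A pre-planned subanalysis of the primary outcome will be performed in the group with baseline thiamine deficiency". The cut-off is fixed: "Thiamine deficiency will be defined as a plasma vitamin B1 level ≤ 7 nmol/L". The paragraph ends with its own caveat: "The trial is not powered to detect subgroup differences, hence this analysis will be considered exploratory and hypothesis-generating".

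The model for the primary outcome is in section 6.2.2. It is a repeated-measures comparison of the arms at 0, 24, 48 and 72 hours with compound symmetry, and "Study site will be controlled for as a fixed-effect in the regression model". Deficiency status does not enter it. Nothing elsewhere in section 6.2 adds an analysis of the non-deficient patients or a comparison of effects between the two groups.

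Section 4.5.1 has all participants sampled at time zero, before study drug. Section 4.5.2 plans thiamine levels without limiting them to any subset.

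**The concern.** The caveat in section 6.2.8 is about subgroup differences, but the analysis it qualifies has one group. A difference in effect needs either an estimate in each group or an interaction term, and neither is described.

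This matters for interpretation. Section 1.4 rests the rationale partly on what happens when thiamine is insufficient, and deficiency is the only effect modifier the protocol names. A reader of the results will want to know whether any benefit is confined to deficient patients or shared by all. A deficient-only estimate cannot separate these. If it is clearly favourable, that fits a benefit in everyone as well as a benefit confined to the deficient. If it is inconclusive, that fits small numbers as well as no effect. The effect in non-deficient patients, which would help to tell these apart, is not among the planned outputs.

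**Working it through.** **Inputs from the protocol**
- Two-sided 5% level, section 6.2.1: "All tests will be two-sided, a p-value < 0.05 will be considered significant".
- Stated power, section 6.1: "at N=80 (40 patients in each arm), we obtained a power of 0.80 at 72-hours".
- Planned 72-hour difference, section 6.1: "observed mean difference (about 0.51", read as mg/dL from the eligibility criterion.
- Enrolment 88, allocation 1:1 (sections 6.1 and 2.2).

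**Assumption.** The share of deficient patients, *p*, is not given. I use 20% to 35% (about 18 to 31 of 88) and show 10% to 50% as a wider range. Section 3.3 excludes known or highly suspected deficiency, which may lower *p*.

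**The plan's own figure.** Simple two-sample formulas with the printed variances (0.19 within, 1.3 between) do not return 0.80 at 40 per arm. The SD of a single 72-hour value, √(1.3 + 0.19) = 1.221, gives 0.46. The SD of a change from baseline, √(2 × 0.19) = 0.616, gives 0.96. These bracket 0.80. The protocol's figure came from a simulation using mean differences at four time points, only one of which is printed, so this shows no error. I therefore take 0.80 as given and back out the SD it implies: 0.51 / [√(2/40) × (1.960 + 0.842)] = 0.814.

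**Step 1: what the deficient-only analysis estimates.** If the true effect is 0.51 in every patient, the expected estimate among deficient patients is 0.51, the same as overall, and the true interaction is 0. The deficient-only result carries no information on the interaction unless it is set against the other group.

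**Step 2: its power at N=88.** With the same effect in everyone, power = Φ(2.802 × √(88/80) × √p − 1.96).
- *p* = 0.20: Φ(1.314 − 1.96) = Φ(−0.646) = 0.26.
- *p* = 0.35: Φ(1.739 − 1.96) = Φ(−0.221) = 0.41.

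Across *p* = 10% to 50% the range is 15% to 55%. For *p* = 20% to 35%, an SD of 1.221 gives 14% to 21%, and an SD of 0.616 gives 41% to 63%.

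**Step 3: precision of the interaction.** With 1:1 allocation and equal variance in both groups, SE(interaction) / SE(overall) = √[1/p + 1/(1 − p)] = 1/√[p(1 − p)].
- *p* = 0.20: 1/√0.16 = 2.50.
- *p* = 0.35: 1/√0.2275 = 2.10.

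The overall SE at 44 per arm is 0.814 × √(2/44) = 0.174.

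| Deficient share | SE of interaction | 95% CI half-width | Power for a 0.51 difference between groups | Difference detectable with 80% power |
|---|---|---|---|---|
| 20% | 0.434 | 0.85 | 22% | 1.22 |
| 35% | 0.364 | 0.71 | 29% | 1.02 |

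Over 10% to 50%, power for a 0.51 difference is 14% to 31%, and the detectable difference runs from 1.62 down to 0.97 mg/dL. The interaction model estimates the right quantity but will not be a powered test.

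**The case against.** The strongest reply is that the protocol never says this subanalysis tests effect modification. The effect of thiamine among deficient patients is a legitimate target, and randomisation supports it in a group defined at baseline. The words "The trial is not powered to detect subgroup differences" can also be read as differences between arms within the subgroup, which is what the preceding sentence plans. This stands as far as it goes: the planned estimate is valid, and the mismatch in wording rests on one of two readings. It does not make a one-group estimate informative about whether the effect differs.

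A second reply is that one subgroup, one cut-off and one outcome are pre-specified, lack of power is admitted and the analysis is called exploratory. That restrains over-reading and keeps the point minor. But the label deals with power and multiplicity, and does not supply the missing comparison.

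A third is that a separate SAP may add the complement and an interaction, and section 6.2.8 does not literally confine itself to deficient patients. That is possible. Section 6.2 is, however, itself titled as the statistical analysis plan, and it fixes the population, outcome and cut-off.

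Two stronger readings are tempting and not supported:
- A reader might treat the chance of significance in step 2 as a false-positive rate and set it against 5%. It is power. In that scenario thiamine does work in deficient patients, and saying so would be correct. The error would be to conclude that it works only in them, which the protocol nowhere plans to do.
- A reader might infer that a significant deficient-only result is to be expected whenever thiamine works equally in all. At 26% to 41% it would be the less likely outcome.

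**Conclusion.** The point holds as a minor one. As described, section 6.2.8 yields a valid but imprecise effect in deficient patients and nothing that bears on whether the effect differs by deficiency. The size rests on three assumptions: a deficient share of 20% to 35%, the stated 80% power at N=80 taken at face value, and all 88 patients analysed. The logic in step 1 needs none of them. A reader might infer that the trial's main result is compromised. It is not: the subanalysis is exploratory and the primary comparison does not depend on it.

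**What to change.** Amend section 6.2.8 to fit the section 6.2.2 model in all analysed patients, adding baseline deficiency (same cut-off) and its interaction with treatment and time. Report three quantities at 72 hours, each with a 95% CI: the effect in deficient patients, the effect in non-deficient patients, and the difference between the two. Keep the exploratory label, and say that a statement about differential effect will rest on the interaction estimate and not on significance in one group.

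The cost is one further model. Baseline thiamine must be measured across participants anyway to identify who is deficient, so no extra sampling is needed. The drawback is a wide interaction interval, about ±0.71 to ±0.85 mg/dL under the assumptions above, which will often leave the question open. An interval of that width still tells the reader plainly how little the trial can say about a differential effect.

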7. DATA COLLECTION AND MANAGEMENT

7.1 Data collection process

Data collection will be the responsibility of the principal investigator. Creatinine and lactate levels will be obtained from blood draws at 0hr, 24hr, 48hr, and 72hr. Most other variables (i.e. demographics, sepsis characteristics and laboratory results) will be obtained prospectively from the electronic medical record up until the time the patient dies or is discharged from the hospital. Data will be entered directly into the online database software (see below).

7.2 Variables

Will be provided on the online CRF.

7.3 Data quality and validity

Several measures are taken to assure data quality. They are as follows:

- 1) Database access is restricted to team members specifically trained in data entry for this study. In addition, team members will only have access specific to their roles and only data abstractors will have the capacity to enter/change data entries.
- 2) The REDCap Cloud database is specifically designed to maintain data integrity by preventing unintentional changes or lost data. Servers back up all data on a nightly basis with redundant systems. The REDCap data management system is fully HIPAA-compliant and includes a complete audit-trail for data entry validation. For additional details, see below.
- 3) Our group has a full-time database manager who will oversee the database and maintain quality. They will perform weekly data checks evaluating for any missing data or other concerns. Weekly reports will be generated on all missing data elements and feedback provided directly to the data abstractors on any issues that are identified. The weekly reports will allow for accounting of all data in real-time and allow for direct feedback to data abstractors such that future recurrences of missing data entry will be minimized. Of note, all missing data will be coded indicating the reason for being missing.

7.4 Data storage and security

The database application we will use is REDCap Cloud (<https://www.redcapcloud.com/>). REDCap Cloud is a professional database that provides a user-friendly interface with capacity for easy statistical interface and is endorsed by the National Institutes of Health. The principal investigator and other members of the Center for Resuscitation Science are experienced with REDCap. The REDCap Cloud data management system is secure, fully compliant with all regulatory guidelines, and includes a complete audit-trail for data entry validation. Through these mechanisms, as well as relevant training for all involved parties, participant confidentiality will be safeguarded. All members of the research team will be required to complete standardized training in REDCap cloud, which will be documented within the software.

The consent form and other trial documents for each participant will initially be stored in a secure, locked place. Following completion of the trial, documents will be maintained for a period of at least 2-years per FDA regulations (or longer depending on local IRB guidelines).

8. ETHICAL CONSIDERATIONS

8.1 Risks and Benefits

8.1.1 Potential benefits

Potential Benefits to Individual Subject: Assuming our hypothesis is correct and our results are comparable to those previously published, individual patients enrolled in our study and randomized to the treatment arm will benefit from the attenuated risk of kidney injury. All patients participating in this study, including those in the placebo arm, may see a future benefit from knowledge gained since many patients who survive an initial episode of sepsis will have a future admission for sepsis.

Potential Benefits to Society: Septic shock remains a highly morbid clinical condition for which there is no specific therapy. Assuming our hypothesis is confirmed, our study will provide strong support for the widespread adoption of Thiamine therapy for patients with septic shock. This, in turn, will significantly improve patient outcomes and potentially reduce the global burden of death due to septic shock.

8.1.2 Potential harms

Study Drug

Vitamin B1 – Vitamin B1 (thiamine) has an excellent safety profile. The only reported potentially serious side effect is an extremely rare anaphylactic reaction (1:250,000 cases) and this might not even be of issue with the current manufactured version of thiamine in the United States. The risk of an anaphylactic reaction was assessed with a vitamin complex dispensed in Europe and it is not known if thiamine was the actual offending agent. However, the 0.0004% theoretical chance of an adverse reaction seen in the European study is incredibly low. In a series of 989 patients in the United States who received intravenous thiamine, none had an anaphylactic reaction and the only reported side effects were minor consisting of transient local irritation, or in one case pruritus (0.093%).⁵⁰ At BIDMC (approximately 600 inpatient beds), thiamine is provided liberally for patients with nutritional deficiency – for example, BIDMC has administered intravenous thiamine in over 8,000 separate patient encounters from 2002 until present. Despite this heavy usage, no adverse reactions have been reported.

Blood Collection

Most participants will have existing venous or arterial catheters in place and we will be able to collect blood from these ports, essentially eliminating the risks associated with blood collection. In the rare

case that a participant does not have an indwelling line, the risk of venipuncture is extremely low, and will not exceed the risk of clinical blood draws the participant will already be receiving.

Loss of Confidentiality

The risk of a privacy and confidentiality breach for all screened and enrolled patients will be minimized at multiple levels. After enrollment, trained research assistants will abstract all of the required data prospectively under the supervision of a research nurse, fellow, or senior investigator. All data will initially be recorded on a paper case report form, which will be stored in a locked file cabinet in a locked room while not in use. Two research assistants will independently enter the data into the secure online database (REDCap). In compliance with HIPPA privacy and security regulations, REDCap contains multiple levels of security including data safety (e.g., restricted access to fields), user safety (e.g. password authentication access), application security (e.g., role-based access to features, access audit trails), and hosting service security (e.g., firewall, secure sockets layer). Taken together, these features ensure access control, audit control, data integrity, user authentication, and transmission security. Data from the present trial will be set up in REDCap to ensure exported datasets are de-identified as defined in the HIPAA privacy regulation [45 C.F.R. §164.514 (b)(2)]. A 21 CFR Part 11 compliance document is available upon request from the software's creators. All study investigators have taken the CITI program exam and are well versed in patient confidentiality.

9. MONITORING

9.1 Institutional Review Board (IRB)

The study is approved by the IRB at BIDMC (#2018P000204).

9.2 Data Safety and Monitoring Board (DSMB)

A DSMB comprised of three physicians with critical care experience in the management of septic patients will be responsible for safeguarding the interests of trial participants, assessing the safety and efficacy of the interventions during the trial, and for monitoring the overall conduct of the clinical trial. An independent biostatistician/epidemiologist will prepare all DSMB reports. The DSMB members will be chosen such to avoid any financial or intellectual conflicts of interest. The DSMB will review deidentified data after every 30 participants are enrolled to assess for safety; unless there are group differences necessitating unblinding (as determined by the DSMB), the DSMB will be blinded to treatment groups. The trial will continue while the DSMB review data. After each review, the DSMB will create a short report to the steering committee with recommendations for continuation, modifications, or termination of the trial. Criteria for recommending termination will be at the discretion of the DSMB and there will be no formal statistical criteria for termination due to efficacy or safety.

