5.4.3 Adverse Event Reporting

All unexpected serious adverse events thought to be related to the study drug, and any unexpected fatal or life-threatening adverse events thought to be related to the study drug will be recorded in the online CRF, reported directly to the coordinating center, and reported to the appropriate IRB shortly following the event per local protocol. In addition, unexpected serious adverse events related to the study drug will be undergo expedited reporting to the DSMB within 7 days of the coordinating center becoming aware of the event. The DSMB will additionally review all adverse events in aggregate after every 50 patients are enrolled.

Adverse events will additionally be reported to the FDA as outlined in 21CFR312.32 and summarized below:

- a. All unexpected fatal or life-threatening adverse events thought to be related to the study drug will be reported to the FDA within 7 calendar-days of when the TRPSS team is made aware of the event.
- b. All unexpected serious adverse events thought to be related to the study drug will be reported to the FDA within 15 calendar-days of when the TRPSS team is made aware.
- c. All serious unexpected adverse events, and any unexpected fatal or life-threatening events thought to be related to the study drug, will be reported back to all site investigators within 15 calendar-days of the event.
- d. The TRPSS team will periodically review all published information relating to the safety of each element of the drug combination. Any concerning safety information obtained from this review, or otherwise obtained (e.g. from unpublished scientific papers), will be reported to the FDA within 15 calendar-days.

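### Protocol 9.2 gives the DSMB an efficacy remit and discretionary termination without a statistical criterion, so early stopping for benefit is not excluded while the final test stays at an unadjusted 0.05

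*Protocol*

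**What the plan says.** Section 9.2 of the protocol describes the board's role in terms that do not agree with each other.

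Pointing to safety monitoring only:
- The purpose of the scheduled reviews: "The DSMB will review deidentified data after every 30 participants are enrolled to assess for safety".
- The default blinding: "unless there are group differences necessitating unblinding (as determined by the DSMB), the DSMB will be blinded to treatment groups".

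Pointing to a role in efficacy:
- The board's responsibilities include "assessing the safety and efficacy of the interventions during the trial".
- After each review it reports to the steering committee with "recommendations for continuation, modifications, or termination of the trial".
- The criteria for recommending termination are left to the board, and "there will be no formal statistical criteria for termination due to efficacy or safety".

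Section 6.2.1 sets the significance level for the whole analysis: "All tests will be two-sided, a p-value < 0.05 will be considered significant". It mentions no interim analysis and no adjustment. The protocol nowhere says that the trial will run to full enrollment regardless of apparent benefit.

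Section 5.4.3 adds a further board review: "The DSMB will additionally review all adverse events in aggregate after every 50 patients are enrolled". It covers adverse events only.

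**The concern.** A board that monitors safety alone can look as often as it likes without affecting the type I error of the efficacy test. A board that may also recommend stopping because the treatment looks effective gives the trial more than one chance to declare benefit. Each such chance spends some of the 5% unless a boundary limits it. Section 9.2 names efficacy as a possible ground for termination and, in the same sentence, removes any criterion for it.

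This is more than a detail left for the statistical analysis plan, because the protocol settles the matter by saying that no formal criterion will apply. An analysis plan that introduced a boundary would contradict it.

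If the trial did stop early for apparent benefit, the final p-value could not be read against 0.05 at face value, and the estimated creatinine difference would tend to be too large. In a trial of 88 participants either would weaken the result.

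**Working it through.** **Inputs from the protocol**
- Final test: two-sided 0.05 (6.2.1), critical value 1.960.
- Planned enrollment: 88 (6.1).
- Reviews after every 30 participants (9.2), so at 30 and 60 before the end.

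**Assumptions, because the protocol is silent**
- The board compares the arms on the primary outcome at both reviews. Section 9.2 names no outcome or test.
- It would stop if the interim two-sided p-value fell below some threshold. The protocol sets none, so a range is shown.
- Stopping is symmetric in direction, and information is proportional to the number enrolled.

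**Method.** Under the null hypothesis the statistics at n = 30, 60 and 88 are jointly normal with mean 0, variance 1 and correlation √(nᵢ/nⱼ):
- 30 and 60: √(30/60) = 0.707
- 30 and 88: √(30/88) = 0.584
- 60 and 88: √(60/88) = 0.826

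Overall error = 1 − P(|Z₃₀| < c, |Z₆₀| < c, |Z₈₈| < 1.960), where c is the critical value for the assumed interim threshold.

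**The plan's own figure first.** If efficacy can never stop the trial, only the last test counts and the error is P(|Z₈₈| > 1.960) = 0.05, as 6.2.1 states.

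**With efficacy stopping possible**

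| Assumed interim threshold | c | Overall two-sided error |
|---|---|---|
| p < 0.05 | 1.960 | 0.1066 |
| p < 0.01 | 2.576 | 0.0582 |
| p < 0.005 | 2.807 | 0.0535 |
| p < 0.001 | 3.291 | 0.0505 |
| no efficacy stopping | – | 0.0500 |

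For the first row, the probability of first crossing is 0.0500 at 30, 0.0331 at 60 and 0.0235 at 88, which sum to 0.1066. A simulation of 1,000,000 trials gave 0.1067.

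**Sensitivity to the information at each look.** Some enrolled participants will not yet have a 72-hour value at a review, and some will drop out. Using 27, 55 and 80 in place of 30, 60 and 88, with p < 0.05 throughout, gives 0.1067, so the result hardly depends on this.

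**Boundary for the fallback remedy.** With p < 0.001 at 30 and 60, a final level of 0.05 gives 0.0505 overall. A final level of 0.0495 brings the total to 0.0500.

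**The case against.** The strongest reply is that 9.2 describes a safety board. The only purpose it gives for the reviews is safety. It schedules no interim efficacy analysis and names no outcome, test or dataset for one. Efficacy appears in a general sentence on responsibilities and again in the sentence on criteria, which can be read as saying that no efficacy stopping is planned. On that reading the final 0.05 is valid. The default blinding also makes routine stopping at p<0.05 an implausible model of how the board would behave.

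Much of this stands. It rules out a stronger reading that a reader might infer: that the trial plans to stop for efficacy, or that its true error rate is 10.7%. The documents support neither. A reader might also count the 50-participant review in 5.4.3 as a third efficacy look. The text does not support that, since that review is confined to adverse events. The differing review intervals, 30 and 50, are a separate matter to reconcile.

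The reply does not close the gap. The protocol never says that efficacy will not stop the trial. Blinding to group labels does not hide the size of a difference between two coded arms, and the board itself decides whether to unblind. A reader cannot tell from 9.2 which role the board has.

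**Conclusion.** The point holds as an inconsistency in 9.2 that leaves error control open. It does not show that error control has been lost. Early stopping for benefit is not excluded, no criterion governs it, and 6.2.1 makes no allowance for it.

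The overall two-sided error lies between 0.05 and about 0.107, according to a threshold that must be assumed. At a threshold of 0.01 or stricter the inflation is under one percentage point (0.0582 − 0.05 = 0.0082). The upper end needs a board that would act on p<0.05 for the primary outcome at both 30 and 60, which the text permits but does not suggest. Overestimation of the effect arises only if the trial actually stops early for benefit.

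The point concerns efficacy alone: discretionary stopping for harm needs no adjustment of the final test. It is worth correcting because a single sentence removes the ambiguity.

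**What to change.** State in 9.2 that the trial will not be stopped early for efficacy. The two-sided 0.05 in 6.2.1 is then valid as written. Keep the board's discretion to recommend termination for harm. Its responsibility for efficacy need not be deleted, because it may have to see efficacy data to weigh benefit against harm; what is excluded is stopping because of benefit.

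If the sponsor wants efficacy stopping to remain possible, pre-specify a Haybittle-Peto limit instead: p<0.001 on the primary outcome at each interim review. With 0.05 at the end the overall error is about 0.0505; a final level of 0.0495 gives 0.05.

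The cost is one sentence and no change in sample size. Under the first option the board gives up informal stopping for efficacy. Under the second it keeps the possibility, but only for a very strong early result.
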